IEC	Independent Ethics Committee
IOP	Intraocular Pressure
IP	Investigational Product
IRB	Institutional Review Board
IRT	Interactive Response Technology
ITT	Intent-to-Treat
LASIK	Laser Assisted in Situ Keratomileusis
logMAR	Logarithm of the Minimum Angle of Resolution
MFD	Maximum Feasible Dose
mg	Milligrams
mL	Milliliters
mmHg	Millimeters of Mercury
MR	Manifest Refraction
NOAEL	No Observed Adverse Effect Level
NTP	National Toxicology Program
OAG	Open Angle Glaucoma
OD	Oculus Dexter (right eye)
OHT	Ocular Hypertension
OS	Oculus Sinister (left eye)
PD	Pharmacodynamic
PI	Principal Investigator: the leading Investigator at clinical site.
PM	Post Meridiem (after midday)
POAG	Primary Open Angle Glaucoma
PRK	Photorefractive Keratectomy
PRO	Patient Reported Outcome
SAE	Serious Adverse Event
SAP	Statistical Analysis Plan
SBI	Skye Bioscience Incorporated
SBI-100 OE	SBI-100 Ophthalmic Emulsion
SD	Standard Deviation
SLT	Selective Laser Trabeculoplasty

Abbreviation or Specialist Term	Explanation
SITA	Swedish Interactive Threshold Algorithm
SUSAR	Suspected Unexpected Serious Adverse Reaction
TEAE	Treatment Emergent Adverse Event
THC	Tetrahydrocannabinol
THC-Val-HS/THCVHS	THC amino acid ester containing valine and hemisuccinate
TM	Trabecular Meshwork
TMF	Trial Master File
US	United States
VS	Vital Signs
α	Alpha
β	Beta
Δ -9-THC	Delta-nine (9)- tetrahydrocannabinol

1. INTRODUCTION

This study will be conducted according to Good Clinical Practice (GCP), as defined by the International Council for Harmonisation (ICH) and the ethical principles underlying and the United States (US) Code of Federal Regulations (CFR), Title 21, Parts 11, 50 and 312 (21 CFR 50, 21 CFR 312) and all applicable government regulations and institutional research policies and procedures.

1.1. Background

1.1.1. Disease

Glaucoma is a chronic neurodegenerative disorder characterized by progressive and irreversible vision loss due to structural and functional damage to the optic nerve head and is the third largest cause of irreversible blindness in the world (Parihar, 2016). Elevated intraocular pressure (IOP) does not result from increased aqueous humor production but rather from reduced aqueous outflow (Kwon, et al 2009).

Management guidelines from the “American Academy of Ophthalmology Preferred Practice Pattern for glaucoma treatment” recommend lowering the IOP towards a target level, which is a value or range of values at which the clinician believes that the rate of disease progression will be slowed sufficiently to avoid functional impairment from the disease (Weinreb, Aung and Medeiros, 2014).

Prostaglandin analogues and β -blockers are the first line therapies and the most commonly used medications for the management of glaucoma. Prostaglandin analogues are the most efficacious class of drops. These drugs reduce IOP by reducing outflow resistance resulting in increased aqueous humor flow through the uveoscleral pathway. β -blockers are the second most efficacious class of drops. However, despite being the best locally tolerated agent, they cause the most systemic side effects (Weinreb, Aung and Medeiros, 2014).

Cannabis is one of the most widely used drugs throughout the world. The psychoactive constituent of cannabis, $\Delta 9$ -Tetrahydrocannabinol ($\Delta 9$ -THC), produces a myriad of pharmacological effects in animals and humans through cannabinoid receptors (CB). Two cannabinoid receptors have been identified and characterized: CB1 and CB2 (Han et al., 2013; Abrams and Guzman, 2015). The predominance of CB1 receptors in the ocular tissues, such as the iris ciliary body and Trabecular Meshwork (TM) (Montero et al., 2005) supports the involvement of a localized IOP-reducing mechanism. Several reports can be found on the topical administration of THC formulated in various oily vehicles (Merritt et al., 1981; Elsohly et al., 1981; Jay and Green, 1983). The anatomy and physiology of the eye, however, present a formidable barrier to the intraocular delivery of drugs through the topical route. This is especially true when a drug is needed to provide neuroprotective activity at the back (posterior segment) of the eye. The combination of precorneal and corneal barriers as well as other physiological barriers results in only approximately 5% to 10% of a topically applied drug reaching the inner ocular tissues (Loftsson and Järvinen 1999; Geroski and Edelhauser, 2000). Therefore, for $\Delta 9$ -THC to show both an IOP-reducing and a neuroprotective effect, it is important for it to permeate through initial layers of the eye to the target tissues (Song and Slowey, 2000; Porcella et al., 2000).

The development of THC as an eye drop is especially challenging because of its poor aqueous solubility and high logP. In view of the challenges in the topical delivery of THC, it is not surprising that there are discrepancies in the literature with respect to the efficacy of topically administered THC. As THC is a lipophilic molecule, it rapidly partitions into the lipophilic corneal epithelia but remains trapped there and fails to efficiently partition out into the more hydrophilic stromal layers, and thus does not reach the intraocular tissues. Therefore, a THC prodrug, SBI-100, was developed to overcome these challenges. SBI-100 is a synthetically modified THC-amino acid ester containing a valine and hemisuccinate, otherwise known as THC-Val-HS. The addition of valine and hemisuccinate to THC has demonstrated improved aqueous solubility, and enhanced ocular tissue permeation characteristics resulting in increased reduction in the IOP compared to THC (Adelli et al, 2017; Elsohly et al, 2014).

1.2. **SBI-100**

Skye Bioscience, Inc. (Skye) is developing SBI-100, a synthetically manufactured proprietary prodrug of $\Delta 9$ -THC, as a treatment for glaucoma. THC is a naturally occurring component of *Cannabis sativa* L. (marijuana) and the primary active ingredient of the plant.

The novel ophthalmic emulsion formulation of SBI-100 (SBI-100 Ophthalmic Emulsion) has been developed to provide local therapy and to improve the ocular bioavailability of THC, reducing the potential for systemic side effects.

As a prodrug, SBI-100 is relatively more hydrophilic than the parent THC compound and achieves better tissue penetration into the different parts/tissues of the eye, including the posterior segment, as observed in nonclinical studies. Compared to the standard-of-care glaucoma treatment, SBI-100 demonstrated superior lowering of IOP in rabbits. Moreover, in an ex vivo model of the human TM, THC demonstrated a reduction of biomarkers related to fibrosis, as well as increased outflow through the TM (i.e., IOP-reducing effect).

1.3. **Summary of Nonclinical Studies**

1.3.1. **Pharmacology**

A number of in vitro and in vivo studies were conducted to establish the mechanism of action and IOP-lowering ability of THC. All nonclinical studies conducted for SBI-100 are described in detail in the Investigator's Brochure (IB).

1.3.2. **Pharmacokinetics**

Multiple nonclinical studies were conducted to evaluate the ocular and systemic pharmacokinetics of SBI-100. Elsohly et al. (2019) evaluated the concentration and distribution of $\Delta 9$ -THC and SBI-100 in rabbits following topical delivery of SBI-100. No $\Delta 9$ -THC or SBI-100 was detected in the brain tissues and plasma in this study. More detailed information is provided within the IB.

1.3.3. **Toxicology**

The toxicity profile of SBI-100 Ophthalmic Emulsion was characterized in Good Laboratory Practice (GLP) compliant studies including an in vitro ocular irritation study, two 14-day toxicity studies in rabbits and dogs with SBI-100 Ophthalmic Emulsion after topical ocular

administration, and 2 in vitro genotoxicity studies (Ames and micronucleus assays). Further, as SBI-100 is a prodrug of THC, toxicology data available from the published literature with THC (mainly from the National Toxicology Program [NTP] database) and from literature related to the Food and Drug Administration's (FDA) approval of Marinol provide further information on a major metabolite of SBI-100. Collectively, this information supports the clinical use of SBI-100 in clinical studies to assess the effect on IOP.

1.4. Clinical Studies

There is an ongoing SBI-100 Ophthalmic Emulsion first-in-human (FIH) study being conducted in a Phase I unit in Australia in healthy human volunteers to establish a safety profile. The FIH trial will evaluate the ocular safety and tolerability of SBI-100 Ophthalmic Emulsion. Importantly, pharmacokinetics of SBI-100 and its metabolites will be evaluated to determine systemic exposure following topical delivery of SBI-100 Ophthalmic Emulsion. These data will be important to future development of SBI-100 Ophthalmic Emulsion in patients with ocular hypertension (OHT) or primary open angle glaucoma (POAG).

1.5. Summary of Potential Risks and Benefits

SBI-100 Ophthalmic Emulsion is an investigational topical ophthalmic study drug and the safety profile in humans has not yet been established.

Although SBI-100 has not been studied in humans, cannabis and THC as IOP-reducing agents have been extensively studied in both animal and human experiments. Prior human studies showed inhalation of cannabis or ingestion of THC demonstrated marked reduction of IOP. However, the duration of IOP-reducing effect was short-lived (approximately 3 to 4 hours) and multiple side effects were noted as a result of high exposure to THC and its metabolites in the plasma ([Hepler and Frank, 1971](#)). These side effects included unwanted psychotropic effects, and decreased blood pressure ([Green, 1998](#); [Crawford and Merritt, 1979](#)). Other human studies also evaluated topical administration of THC dissolved in mineral oil. These studies did not demonstrate any reduction of IOP, and multiple patients withdrew as a result of intolerance to the eye drops ([El-Remessy et al., 2003](#)). These poor results from topical administration are likely due to the lack of ocular bioavailability from the mineral oil formulation of THC. Nonclinical studies have demonstrated the neuroprotective benefits of THC in multiple glaucoma models ([El-Remessy et al., 2003](#)).

In nonclinical studies, SBI-100 was well tolerated across animal species at multiple dose levels. IOP was observed to be lowered with reduced systemic exposure to SBI-100, THC, or its metabolites.

Based on nonclinical study results, there is the potential that topical administration of SBI-100 Ophthalmic Emulsion in humans may cause a positive drug test (in urine) and redness around the eyes after administration.

More information about the known and expected benefits and risks and reasonably expected adverse events of SBI-100 Ophthalmic Emulsion may be found in the IB.

1.6. COVID-19 Risk Assessment

The risks of patient involvement in study SBI-100-201 will be assessed in the context of the ongoing global coronavirus disease (COVID-19) pandemic and applicable precautionary response measure in place the local or national level. Risks to patients will be assessed against the anticipated benefit of the study participation in accordance with ICH GCP E6 (Principle 2.2), and risks to quality will also be assessed in accordance with ICH GCP E6 (Section 5). Clinical trial management requirements for study SBI-100-201 will also be assessed against FDA on the management of clinical trials during the COVID-19 pandemic.

Skye Bioscience, Inc. and its Investigators will establish measures to ensure that the conduct of study SBI-100-201 prioritizes the safety of patients and the integrity of clinical data. These measures will be based on a risk assessment of the impact of COVID-19 on patient safety and on clinical trial conduct. If specific measures need to be established at the study level or at a specific site, details will be documented in the Skye Bioscience Trial Master File (TMF).

2. STUDY OBJECTIVES AND PURPOSE

Study objectives and endpoints are presented below. The primary endpoint will be assessed at Day 14. Secondary endpoints will be assessed at all time points.

2.1. Primary Objectives and Endpoints

2.1.1. Primary Objectives

- To evaluate the diurnal ocular hypotensive efficacy of 2 dose levels of SBI-100 Ophthalmic Emulsion compared to placebo in patients with elevated IOP
- To evaluate the ocular and systemic safety of SBI-100 Ophthalmic Emulsion in patients with elevated IOP

2.1.2. Efficacy Endpoints

- Change from Day-1 in mean diurnal IOP at Day 14, in the study eye (see [3.2.2](#)) for 0.5% SBI-100 Ophthalmic Emulsion compared to placebo
- Change from Day-1 in mean diurnal IOP at Day 14, in the study eye (see [3.2.2](#)) for 1.0% SBI-100 Ophthalmic Emulsion compared to placebo

2.1.3. Safety Endpoints

- Change from baseline in vital signs including heart rate and blood pressure
- Change from baseline in safety labs
- Adverse Events (overall, ocular, and non-ocular)
- Change from baseline in ophthalmic assessments – slit lamp biomicroscopy, dilated fundus exam, BCVA, pupil diameter, visual field and pachymetry

2.2. Secondary Objectives

- To evaluate the ocular hypotensive efficacy at individual time points of SBI-100 Ophthalmic Emulsion in patients with elevated IOP
- To evaluate the application comfort of SBI-100 Ophthalmic Emulsion

2.2.1. Efficacy Endpoints

- Time matched change in IOP from baseline IOP at 08:00, 10:00 and 16:00 hours on Day 1, Day 7, and Day 14
- Difference in change from 8:00 in IOP (mmHg) at 10:00 and 16:00 between Pre-dose (Day -1) and Post-dose visits (Day 1, Day 7, and Day 14)

2.2.2. Safety Endpoints

- Assesses changes in Ocular Comfort Patient Reported Outcome (PRO) from Day 1 pre-dose

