Randomization			X						Via IRT after 08:00 IOP confirms eligibility
On-site Dosing			X		X		X		AM dose administered following 08:00 IOP. Treatment provided as a single use vial for binocular instillation BID. AM around 08:00 and PM around 20:00. Dose should be separated by 12 hours. Patient may self-administer PM dose on days 1 and 7.

	Visit 1	Visit 2	Visit 3	Visit 4	Visit 5	Visit 5a	
If not treatment naïve must wash-out of IOP-lowering therapy prior to Day-1.	Screening / Wash-out (D-35 to -2)	Day -1	Day 1		Day 7	Day 14	Day 14 – PM dose to occur on-site with EOS procedures following. Patient to self-administer PM dose if EOS procedures to occur on separate day. Procedures listed in EOS/ET are to be performed for any early terminations
Ocular Comfort PRO			S	S	S		Applies to AM dose occurring on-site. Pre-dose and immediately after drop instillation up to 2 mins, 5m±2m and 10m±5m post-dose. If at 10 min, PRO rating has not returned to the visit day pre-dose value, administer every 30 minutes until pre-dose value is achieved.
Kit Dispensing /Return			D	D/R	R	R	Day 1: patient education on drop instillation, handling, and storage. Return: used and un-used vials must be returned. Dispensing: discuss with the patient IP expectations and diversion prevention. Return: Staff must review with the patient vial level use and determine reasons for missed doses.
Prior/Concomitant Medications	X	X	X		X	X	
Adverse Events	X	X	X		X	X	Assessments performed outside of scheduled visits due to an adverse event should be captured as unscheduled visits.

H = hour (s), m = minute(s), S = serial procedures, D = Dispense, R = Return

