8.3.9. Ocular Comfort Assessment PRO

Interviewer administered Ocular Comfort Assessment in the form of a PRO (see Section 15) is a snapshot of patient's ocular comfort (in both eyes) at the moment of administration. Patients should be educated on how to appropriately rate their level of ocular comfort on the scale at the Day 1 visit prior to the first administration of the PRO. This education should be repeated as needed at the investigators / PRO interviewers' discretion. However, great care must be taken to not unduly influence the outcome.

Prior to study treatment instillation (pre-dose), the PRO should be administered to assess the patient's current ocular comfort level.

Post-dose the PRO is to assess the ocular comfort in relation to drop instillation.

The PRO will only be administered during the AM dosing on Days 1, 7 and 14.

Trained site staff will administer the PRO pre-dose, immediately after drop instillation up to 2 minutes after instillation, 5 minutes (± 2 minute) and 10 minutes (± 5 minutes). If at the 10-minute time point the patient's comfort has not returned to that day's pre-dose value, the PRO should be administered every 30 minutes until the pre-dose value is achieved. The same trained interviewer should administer the PRO for a patient throughout a visit.

Investigator may use their discretion to perform ophthalmic assessments in addition to the PRO should the discomfort be persistent. Investigators should assess for adverse events if a patient's PRO values represent a grade change of 2 or more from that day's pre-dose values.

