10.4.1. General Considerations

Descriptive summary statistics will be provided for demographics and other baseline characteristics, disposition, and dose exposure. The number and percentage of patients who discontinued from the study, along with reasons for discontinuations, will be tabulated and described in listings.

Continuous data will be summarized using descriptive statistics (number of patients, mean, standard deviation, median, minimum, and maximum) and, where appropriate, graphic representation, and two-sided 95% confidence interval (CI); categorical data will be summarized by sample size and proportions.

Data summaries will be provided for the values at each scheduled visit, as well as changes from baseline at each scheduled visit. Baseline is defined as the last measure prior to the initiation of study treatment. For endpoints measured multiple times per day (e.g., IOP), there may be

multiple, time-specific baseline measures. Changes from baseline will use the time-specific baseline where applicable. For safety endpoints, data from unscheduled visits will be included in summaries of the worst-case post-baseline measure within each eye (for ocular data) or patient. Unscheduled visits will not be analyzed for efficacy endpoints.

The study eye will be determined for efficacy analysis purposes. The study eye will be defined as the eye with the highest mean diurnal IOP from the three measures taken on Day-1 (baseline). In the case of a tie, the study eye will be the right eye.

Unless otherwise specified, continuous variables will be analyzed using analysis of covariance (ANCOVA) at the two-sided 0.05 level at a visit. If data consists of multiple visits, mixed model with repeated measurement (MMRM) will be utilized. Categorical variables will be analyzed using the chi-square tests at the two-sided 0.05 level. Additional statistical methodology, sensitivity analyses accounting for missing data, and adjustments for covariates, if any, will be described in the SAP.

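### On Days 7 and 14 the only comfort endpoint, change from Day 1 pre-dose, adds pre-dose drift to the effect of the drop, so it does not isolate application comfort

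*Protocol*

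**What the plan says.** Section 2.2 sets the objective: "To evaluate the application comfort of SBI-100 Ophthalmic Emulsion". The only endpoint attached to it is in Section 2.2.2: "Assesses changes in Ocular Comfort Patient Reported Outcome (PRO) from Day 1 pre-dose".

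Section 8.3.9 describes the measurement. "The PRO will only be administered during the AM dosing on Days 1, 7 and 14", with a pre-dose rating at each of these visits. On the ratings after the drop it says: "Post-dose the PRO is to assess the ocular comfort in relation to drop instillation".

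Two working rules use the same visit's pre-dose rating as their reference. Table 2 (repeated in Sections 7.3 to 7.5 and 8.3.9) continues the ratings every 30 minutes if at 10 minutes the "PRO rating has not returned to the visit day pre-dose value". Section 8.3.9 asks for an adverse event assessment at "a grade change of 2 or more from that day's pre-dose values".

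For analysis, Section 10.4.1 gives the general rule: "Baseline is defined as the last measure prior to the initiation of study treatment". Section 10.4.3 names a within-day contrast for IOP. It says that comfort will be analysed continuously and categorically in a similar way, names no reference for it, and leaves the details to the SAP.

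The post-dose timings in Section 8.3.9 include "5 minutes (± 2 minute) and 10 minutes (± 5 minutes").

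**The concern.** The objective, the stated purpose of the post-dose rating and both working rules concern what a drop does to comfort at the visit where it is given. The endpoint instead measures every later rating against a single value taken before the first dose. Patients dose twice daily at home between visits (Section 3.1), so the Day 7 and Day 14 pre-dose ratings are taken on treatment and may have moved. Section 1.5 names redness around the eyes as a possible effect, so some drug-related movement is conceivable.

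If it occurs, a difference between arms at Day 7 or 14 could not be attributed to the drop from this endpoint alone. Drift could make a well-tolerated drop look uncomfortable, or hide discomfort that the drop does cause.

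**Working it through.** The plan states no figure for this endpoint, so there is none to reproduce. The check is an identity.

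**Inputs.** Let pre_d be the pre-dose rating on day d and post_d a post-dose rating that day, with d = 1, 7 or 14 (Section 8.3.9). The endpoint is post_d − pre_1 (Section 2.2.2).

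**Identity.**

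post_d − pre_1 = (post_d − pre_d) + (pre_d − pre_1)

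The first term is the change across that visit's drop. The second is the drift in the pre-dose rating since Day 1.

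- Day 1: pre_d = pre_1, the second term is zero, and the endpoint is the drop effect alone.
- Days 7 and 14: the endpoint is the drop effect plus drift.

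**Between arms.** Active minus placebo on the endpoint = (difference in drop effect) + (difference in drift). Drift shared by the arms cancels; differential drift stays. Adjusting for the Day 1 rating in ANCOVA or MMRM does not remove it, because it arises after Day 1.

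**Single patients (illustrative ratings).**

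| pre_1 | pre_14 | post_14 | Endpoint (post_14 − pre_1) | Same-visit change (post_14 − pre_14) |
|---|---|---|---|---|
| 0 | 2 | 2 | 2 | 0 |
| 2 | 0 | 2 | 0 | 2 |

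The first patient shows a two-grade endpoint change but does not meet the Section 8.3.9 check. The second meets the check but shows no endpoint change.

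**Size, on assumed values.** Take a true active-minus-placebo drop effect of 0.5 grade.

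| Difference in drift | Day 1-referenced contrast | Same-visit contrast |
|---|---|---|
| −1 | −0.5 | 0.5 |
| −0.5 | 0.0 | 0.5 |
| 0 | 0.5 | 0.5 |
| +0.5 | 1.0 | 0.5 |
| +1 | 1.5 | 0.5 |

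Now take no drop effect, an SD of change of 1 grade, 17 patients per arm and a two-sided 0.05 t-test. A drift difference of 0.25, 0.5 or 1 grade gives a significant Day 1-referenced contrast with probability 0.11, 0.29 or 0.81. Such a result would be a correct finding about total comfort; the error would lie in reading it as an effect of application.

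**Does another section supply the same-visit contrast?** Section 10.4.1 does not. Its baseline must precede the start of treatment, which a Day 7 or Day 14 pre-dose rating cannot do, even as a time-specific baseline. Section 10.4.3 spells out a within-day contrast for IOP only.

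**Windows.** 5 ± 2 minutes is 3 to 7; 10 ± 5 minutes is 5 to 15. They overlap from 5 to 7 minutes, so two compliant readings can be taken moments apart.

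**The case against.** The strongest reply is that the endpoint is listed under safety, follows the protocol's general baseline rule, and in a randomised comparison estimates the total effect of treatment on comfort. A patient who is worse both before and after the Day 14 drop has deteriorated on treatment, and a safety endpoint should count that. This stands. A reader might infer that the endpoint is biased, or that it fails to measure application comfort at all. The documents support neither: the Day 1-referenced contrast is valid for its own question, Day 1 is unaffected, and on later days the drop effect is still one component.

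A second reply is that Section 10.4.1 promises summaries of values at each visit, from which a mean same-visit change could be obtained by subtraction if pre-dose and post-dose ratings are both tabulated, and that the SAP may add the contrast. This stands in part. But the protocol itself fixes the reference in its endpoint list, and an SAP that follows it faithfully reproduces the mismatch. Nor are the same-visit values purely operational: through the adverse event check, drop-related discomfort can reach the safety data.

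A reader might also infer a loss of precision large enough to express as extra patients. Assumed correlations of 0.7 to 0.8 within a visit and 0.4 to 0.5 between visits give an SD ratio of √[(1 − r_b)/(1 − r_w)] = 1.29 to 1.73 for raw changes. With the pre-dose rating as a covariate it is √[(1 − r_b²)/(1 − r_w²)] = 1.21 to 1.53. The protocol gives no comfort SD or correlation, and its sample size rests on IOP alone, so no multiplier should be claimed.

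On the windows, the form in Appendix 1 records the time of each rating and one interviewer serves the whole visit. Reversed order is therefore unlikely, and the same rule applies in every arm.

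**Conclusion.** The point holds as a mismatch between objective and endpoint. On Days 7 and 14 the sole comfort endpoint measures total comfort change on treatment and does not isolate application comfort. This follows from the definitions and needs no assumption.

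How much it matters depends on differential pre-dose drift, whose size and direction the document does not give. The rating scale is also not visible in the copy at hand, so the grade examples are illustrations only. The point concerns a secondary endpoint in a study that Section 10.4.6 calls hypothesis-generating; the primary IOP analysis and the sample size are untouched. The change is worth making because it costs very little and lets the stated objective be answered at all three visits. The window overlap is a separate and minor matter.

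**What to change.** In Section 2.2.2, define application comfort on Days 1, 7 and 14 as the post-dose rating minus the pre-dose rating of the same visit. Keep change from Day 1 pre-dose, including change in the pre-dose rating itself, as a separate endpoint labelled cumulative tolerability. Carry both definitions into the SAP. No new data or visits are needed; the cost is a short wording change and one more comfort summary.

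Separately, make the 5-minute and 10-minute windows non-overlapping wherever they are stated: Table 2, Sections 7.3 to 7.5 and Section 8.3.9. With the 5-minute window ending at 7 minutes, any tolerance below 3 minutes on the 10-minute reading does this (10 − 3 = 7). The cost is slightly tighter timing at sites.
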